9.1. Study Visit and Assessment Timing

During the study, the evaluation and follow-up visits must be performed 7 (+ 1) and 10 (+2) days after the initial application of the test product, respectively.

9.2. Demographic/Medical History Assessments

The following demographic parameters will be captured: date of birth, gender, race, size of household, and hair characteristics (length, texture, and curliness). Medical history and current medication usage will be assessed as related to the eligibility criteria listed in chapter 8.6.

9.3. Efficacy

9.3.1. Assessment of Hair and Scalp

An assessment of the hair and scalp will be performed with nit comb (dry combing) to determine the number of live lice observed pre- and post-treatment (Visits 1 to 4). An estimate of the number of apparently live nits will be made prior to treatment only. Each assessment will count the number of live lice and nits observed in the left, middle, and right side of the head.

9.4. Safety

9.4.1. Global tolerability assessment

Global tolerability (general well-being and comfort of the subject) will be assessed by blinded study staff and by the subject or his/her guardian at day 10. The study staff will perform the rating in each case prior to the assessment by the subject to avoid bias. Afterwards, the subject will self-assess the global tolerability. The global tolerability will be rated on a 4-category scale with:

- Score 1 = very good
- Score 2 = good
- Score 3 = moderate
- Score 4 = poor

9.4.2. Local tolerability assessment

Subjective symptoms (burning, paraesthesia, pruritus) after administration of the investigational products will be rated by the subjects on a 4-category scale at day 0 (0h, 1h p.a.) and day 7 (0h, 1h p.a.) directly after study drug application, day 1 (24h), and day 10 p.a.:

- Score 1 = none
- Score 2 = mild
- Score 3 = moderate
- Score 4 = severe

It will be investigated, whether the treatments have any influence on the above mentioned subjective symptoms.

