2. INTRODUCTION

Head lice (*Pediculus humanus capitis*) are parasitic insects that can be found on the head, of humans, particularly school age children. Head lice are tiny, wingless insects (2-3 mm in length) which live among the warmth of human hair, usually close to the scalp, and feed from the blood in the scalp. They crawl but cannot fly or hop. Although small, head lice can be seen with the naked eye. However, a magnifying glass may facilitate observation. When head lice bite the scalp to feed on the blood, it may cause itching; when lice crawl, it can cause a tickling/itching sensation. Lice are also more active in the dark, disrupting the infested person's sleep.

Female lice lay 3-5 eggs (also called nits) per day, which take 1-2 weeks to hatch. Nymphs need 7-10 days to become adult lice. Head lice infest the head and neck and the nits attach to the base on the hair shaft, generally within $\frac{1}{4}$ inch of the scalp. Head lice survive on the human host for up to 30 days.

Lice are spread by direct contact with an infested individual or contact with clothing, worn by the infested individual, or with personal items (e.g., hair brushes, hair ties, towels, bed linens, etc.). Personal hygiene or cleanliness has nothing to do with getting lice. There is no evidence that lice prefer clean or dirty hair or whether the length of the hair increases the risk for being infested with lice. Head lice do not carry diseases, nor can they survive on non-humans (e.g. pets do not transmit). When removed from the human host, head lice usually die within 24 hours. Also, when lice are in water, they become extremely inactive but remain firmly attached to the hair. For this reason, lice are generally not transmitted in the swimming pool; however, sharing the towel, used to dry the hair of the infested individual, may contribute to transmitting head lice.

Head lice are very common; about 10% of the population are infested. From 6 to 12 million infestations occur in the United States each year in children aged 3 to 12 years of age. It occurs more frequently in girls than boys. It occurs less frequently in African Americans than other races; this might be explained by the shape and thickness of the hair shaft.

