5.2. Secondary objectives

Secondary objectives refer to comparison of the cure rate of test product with those of reference product using the following endpoints:

Secondary efficacy objectives:

- a) To show that the cure rate at the end of day 10 (corrected for re-infestation) for the reference product for all baseline infestations is better than 70%.
- b) To show that the test product has a cure rate superior to that of the reference product.
- c) In case that superiority cannot be shown: to show that the test product is non-inferior to reference product regarding cure rate. A non-inferiority margin of 7.5% will be used.

Further secondary objectives refer to objectives c and d, however evaluated in subgroups or other time points.

- d) Efficacy of the investigational products for head lice for mild and moderate baseline infestations (cure rate at the end of the study day 10, corrected for re-infestation).
- e) Efficacy of the investigational products for head lice for all baseline infestations (cure rate at day 1).
- f) Efficacy of the investigational products for head lice for mild and moderate baseline infestations (cure rate at day 1).

As further secondary objectives, safety and tolerability of test product or reference as well as the acceptance of the investigational products will be evaluated.

Secondary safety objectives;

- g) To evaluate local tolerability by subject: subjective symptoms (burning, paraesthesia, pruritus): 0h, 1h, 24h, 7d and 10d p.a. (descriptive evaluation).
- h) To evaluate global tolerability by the subject and study staff (number of subjects with global tolerability ratings of “very good”, “good”, “moderate”, “poor”, descriptive evaluation) at 10d

after application.

- i) To evaluate skin irritation by study staff (secondary infection, erythema, excoriation) on day 0, 1, 7 and 10.
- j) To evaluate eye irritation by study staff on day 0, 1, 7 and 10.
- k) To evaluate characterization of safety and tolerability of the investigational products considering Adverse Events in the study population.

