5.3. Endpoints

The primary endpoint is the cure rate at the end of day 10 (corrected for re-infestation) for the test product for all baseline infestations.

The secondary endpoint is the difference of cure rates (as defined as primary endpoints) between both treatments.

Safety endpoints are the secondary characteristics of the lice infestation (see Section 9.4) and reported adverse events.

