If household members exhibit infestation with lice or nits, they will be offered the opportunity to participate in the study or will receive the standard of care if they choose not to participate in the study. In addition, household members will be advised to wash bed linens, towels, and brushes or combs used on the hair to prevent reinfestation.

To sum up, at visit 1, the following operations will be performed and/or parameters controlled by the study team:

- Age-appropriate subject information and obtaining of written informed consent
- Documentation of demographic data
- Documentation of medical history
- Documentation of pre-existing or concomitant medication
- Verifying of head lice infestation, incl. severity

- Checking of inclusion and exclusion criteria including pregnancy test if applicable
- Decision regarding study inclusion, randomisation
- Baseline assessments (including local tolerability before treatment)
- First application of the investigational product

- Post-treatment assessments (local tolerability, skin and eye irritation, adverse events) directly after start of treatment, as well as 1 hour after removing the investigational product
- Questionnaire on the satisfaction with esthetical effect of the products

After the assessments, the subject is released from the clinical ward and advised to follow the instructions / restrictions made in the protocol and to come back on the next day for the second visit.

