9.4.3. Skin irritation assessment

Skin irritation (secondary infection, erythema, pruritus, excoriation) will be assessed by blinded and trained study staff within 1 hours before first treatment (baseline), as well as directly after study drug

application and after the end of treatment on study day 0, day 1, day 7 (pre-treatment, 0h and 1h p.a.) and on day 10. For the assessment of skin irritation, the following 4-category scale will be used:

- Score 1 = no
- Score 2 = mild
- Score 3 = moderate
- Score 4 = severe

It will be investigated, whether the investigational products may cause symptoms of skin irritation.

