10.5. Safety Analyses

Safety analyses will be performed in the Safety Population, including all enrolled subjects who administered the investigational product, independently of the duration of treatment.

Safety data will be presented in tabular and/or graphical format and summarized descriptively. A comparison of the secondary characteristics of the lice infestation (see chapter 9.4) will be performed along with tabulation of the reported adverse events.

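### Pruritus is scored as product tolerability although lice cause itch, and the plan neither lists the pre-treatment rating consistently nor says how it is used

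*Combined protocol and SAP*

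**What the plan says.** **Cause of itch.** Section 2 says "When head lice bite the scalp to feed on the blood, it may cause itching", and adds that crawling lice can also produce tickling or itching. Inclusion criterion 4 requires at least 5 live lice.

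**Use of itch as tolerability.** Section 9.4.2 has subjects rate burning, paraesthesia and pruritus from 1 (none) to 4 (severe), and states: "It will be investigated, whether the treatments have any influence on the above mentioned subjective symptoms". Section 9.4.3 has blinded staff rate pruritus again, beside secondary infection, erythema and excoriation, and states: "It will be investigated, whether the investigational products may cause symptoms of skin irritation". (Objective i, on skin irritation, does not name pruritus.) Section 5.3 describes the same items differently: "Safety endpoints are the secondary characteristics of the lice infestation (see Section 9.4) and reported adverse events".

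**Rating times.** The visit 1 list in 6.2 includes "Baseline assessments (including local tolerability before treatment", and the Time and Events Table in 6.7 marks local tolerability in its -1H column. Objective g in 5.2 lists "subjective symptoms (burning, paraesthesia, pruritus): 0h, 1h, 24h, 7d and 10d p.a. (descriptive evaluation", and 9.4.2 puts the ratings "at day 0 (0h, 1h p.a.) and day 7 (0h, 1h p.a.) directly after study drug application", followed by Day 1 and Day 10.

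**Analysis.** Section 10.5 says "Safety data will be presented in tabular and/or graphical format and summarized descriptively". It adds that the 9.4 items will be compared, without naming a method.

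**The concern.** The plan asks one pruritus score to answer two questions: is the subject still bothered by lice, and does the product irritate? It gives no rule for telling these apart. Two consequences follow.

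- Itch present before the first application, or caused by lice that survive to Day 7, can be reported as intolerance of the product in either arm.
- On Days 7 and 10, an arm that clears fewer lice can show more itch for that reason alone. At the cure rates the plan assumes, this would favour the test product.

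At stake are the local tolerability objective (g) and the pruritus part of the 9.4.3 skin irritation assessment. The primary endpoint is not affected.

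**Working it through.** **1. Where a pre-application symptom rating is listed**

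| Place | Day 0, before application | Day 7, before second application |
|---|---|---|
| 5.2, objective g | not listed | a 7-day time is given, without saying before or after the second application |
| 6.2, visit 1 list | listed | – |
| 6.4, visit 3 list | – | local tolerability listed, timing not stated; only skin and eye ratings are placed before application |
| 6.7, table | marked at -1H | one mark for the visit, timing not stated |
| 9.4.2 | not listed | not listed; 0h and 1h after application only |
| 9.4.3, skin irritation (includes staff-rated pruritus) | listed | listed |

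The subject-rated baseline is therefore contradictory on Day 0 and not explicit on Day 7. The staff-rated skin score is explicit on both days. As 6.7 reads in the available text, local tolerability is marked at -1H and +1H on Day 0 but not at 0, whereas objective g and 9.4.2 include 0h. The table may have suffered in conversion, so this needs only a check.

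**2. Figures available**

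The documents give no figure for tolerability. The usable planning figures are the cure rates of 95% (test) and 55% (reference) in 8.1 and 10.2. They are the rates behind the 30 per group in 10.2, which reproduces with a one-sided 5% level, 80% power and a 15-point margin:

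[0.95×0.05 + 0.55×0.45] × (1.645 + 0.842)² / (0.40 − 0.15)² = 0.295 × 6.18 / 0.0625 = 29.2, rounded up to 30.

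**3. Day 10 itch from residual infestation alone**

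Let c be the cure rate, and a and b the prevalence of pruritus in uncured and cured subjects. With no product effect:

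prevalence in an arm = c·b + (1 − c)·a

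gap (reference minus test) = (0.95 − 0.55)·(a − b) = 0.40·(a − b)

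The values of a and b are assumptions; the documents give none.

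| a (uncured) | b (cured) | Test | Reference | Gap, points |
|---|---|---|---|---|
| 20% | 20% | 20.0% | 20.0% | 0 |
| 30% | 10% | 11.0% | 19.0% | 8 |
| 50% | 20% | 21.5% | 33.5% | 12 |
| 50% | 10% | 12.0% | 28.0% | 16 |
| 60% | 10% | 12.5% | 32.5% | 20 |
| 70% | 10% | 13.0% | 37.0% | 24 |
| 80% | 10% | 13.5% | 41.5% | 28 |

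With 35 per arm, the 50%/10% row means 35×0.12 = 4.2 against 35×0.28 = 9.8 subjects with itch.

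**4. Does subtracting baseline remove this gap?**

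Assume 50% itch at baseline in both arms, itch that persists in every uncured subject who had it, itch that persists in 20% of cured subjects who had it, and no product effect.

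- Test, Day 10: 0.50 × (0.05 + 0.95×0.20) = 12%; change 12 − 50 = −38 points.
- Reference, Day 10: 0.50 × (0.45 + 0.55×0.20) = 28%; change 28 − 50 = −22 points.
- Gap: 16 points as observed and 16 points as change from baseline.
- Subjects worse than their own baseline: 0% in each arm.

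Mean change leaves the gap untouched, because it comes from differential cure. Counting subjects who worsen removes it in this model. With real product irritation that count is not clean either: a cured subject who moves from 3 to 2 shows no worsening even if the remaining itch comes from the product.

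**5. The times closest to application**

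From just before application to 0h and 1h, clearance of lice has had little time to act. A comparison with the immediate pre-application score is the cleanest reading of product effect in the schedule. On Day 7 it needs a symptom rating that the plan does not explicitly schedule.

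**The case against.** The other side has several good points.

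- **Nothing says that baseline will be ignored.** A reader might infer that raw scores will be reported without the pre-treatment value. Section 10.5 does not say so; a by-visit table that includes baseline would satisfy it. What stands is that no use of baseline is specified.
- **Leaving out baseline does not create the arm difference.** A reader might infer that it does. Allocation is randomised 1:1, so baseline itch is balanced in expectation, and step 4 shows the same gap on both scales.
- **Not every sign is a lice effect.** The label in 5.3 invites that reading, but the introduction names only itching and tickling. Erythema, excoriation, secondary infection, burning, paraesthesia and eye redness are not individually attributed to lice. The point is confined to pruritus. Likewise, the documents do not say that diagnostic combing irritates the scalp.
- **The wording of 9.4.2 is neutral.** An influence on symptoms can include relief of itch. That is fair, but the section sits under safety and gives no rule for reading the score either way.
- **A baseline-relative route exists for adverse events.** Section 9.5.3.1 counts worsening of conditions present at entry, and 9.8 records pre-treatment signs that deteriorate. This softens the concern but does not govern the scored tolerability items.
- **The illustration is simplified.** It treats cured as lice-free, whereas 9.5 corrects cure for re-infestation and allows up to two adult lice or third-stage nymphs on Day 10. Combing also lowers louse numbers in both arms. Both would tend to narrow the gap.

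**Conclusion.** The concern holds for pruritus, in two parts.

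The first part rests on the text alone. The rating times contradict each other for Day 0, the symptom rating before the Day 7 application is not explicit, and the analysis section gives the pre-treatment scores no role. If 9.4.2 is followed as written, itch after the second application cannot be separated from itch due to surviving lice, and a rating not taken cannot be recovered later.

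The second part is conditional. If cure rates differ and uncured subjects itch more than cured ones, Day 7 and Day 10 pruritus can make the lower-cure arm look less tolerable. At 95% and 55% cure with no product effect, the Day 10 gap runs from 0 to 28 points over the assumed prevalences, and it is zero if cured and uncured subjects itch equally. The plan gives no Day 7 cure rates, so the Day 7 effect is not sized.

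The documents do not support saying that tolerability results will be wrong, only that they can be misread. These are secondary endpoints and objective g is explicitly descriptive. The change is still worth making because it costs little and part of it must precede data collection.

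**What to change.** 1. **Rating times.** Add the Day 0 pre-treatment local tolerability rating to objective g and 9.4.2, so that they agree with 6.2 and 6.7. Add an explicit symptom rating before the Day 7 application in 6.4, 6.7 and 9.4.2. Check the 0h mark for local tolerability in 6.7 at the same time.
2. **Main tolerability result.** In 10.5, define it for each item as worsening from the subject's own immediate pre-application score to 0h and 1h, on Day 0 and on Day 7, shown as shift tables by arm.
3. **Later times.** Show Day 1, Day 7 pre-treatment and Day 10 scores as shifts from the Day 0 pre-treatment score, with a descriptive display by live lice present or absent. State that arm differences at these times may reflect residual infestation, and that relief of lice itch can mask itch from the product.

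**Cost.** Wording changes, a different table layout and one extra symptom rating on Day 7; the other data are already collected. The split by live lice conditions on a post-randomisation outcome, so it should stay descriptive. A subject already at score 4 cannot worsen; shift tables make such cases visible.

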9.4.3. Skin irritation assessment

Skin irritation (secondary infection, erythema, pruritus, excoriation) will be assessed by blinded and trained study staff within 1 hours before first treatment (baseline), as well as directly after study drug

application and after the end of treatment on study day 0, day 1, day 7 (pre-treatment, 0h and 1h p.a.) and on day 10. For the assessment of skin irritation, the following 4-category scale will be used:

- Score 1 = no
- Score 2 = mild
- Score 3 = moderate
- Score 4 = severe

It will be investigated, whether the investigational products may cause symptoms of skin irritation.

9.4.4. Eye irritation assessment

To investigate a potential irritation of the eyes due to the treatment, the trained and blinded study staff will be assessed the severity of redness on both eyes (left, right) within 1 hours before first treatment (baseline), as well as directly after study drug application and after the end of treatment on study day 0, day 1, day 7 (pre-treatment, 0h and 1h p.a.) and on day 10. For the assessment of eyes, the following 4-category scale as mentioned above will be used.

- Score 1 = no
- Score 2 = mild
- Score 3 = moderate
- Score 4 = severe

It will be investigated, whether the investigational products may irritate the eyes.

9.4.5. Vital Signs

Vital sign measurements will include systolic and diastolic blood pressure and pulse rate after the subject has rested in a seated position for at least 5 minutes. These will be recorded at each visit.

9.4.6. Urine Pregnancy Test

A urine pregnancy test will be performed at the screening visit (Day 1) and day (10) to ensure all females of child-bearing potential are NOT pregnant.

9.4.7. Assessment of esthetical properties

The esthetical properties of the investigational products will be evaluated to determine the satisfaction by the subjects with the products after application using a questionnaire about hair and scalp feeling, greasiness, hair look, shininess and volume. The questioning will be performed on day 0 and day 7 after treatment and drying the hair.

1. Your hair does not feel too dry after treatment.

- Score 1 = strongly agree
- Score 2 = agree
- Score 3 = disagree
- Score 4 = strongly disagree

2. Your scalp feels pleasant after treatment.
 - Score 1 = strongly agree
 - Score 2 = agree
 - Score 3 = disagree
 - Score 4 = strongly disagree
3. The greasiness of your hair after treatment is normal.
 - Score 1 = strongly agree
 - Score 2 = agree
 - Score 3 = disagree
 - Score 4 = strongly disagree
4. Your hair looks good after the treatment.
 - Score 1 = strongly agree
 - Score 2 = agree
 - Score 3 = disagree
 - Score 4 = strongly disagree
5. The shininess of your hair after treatment is fine.
 - Score 1 = strongly agree
 - Score 2 = agree
 - Score 3 = disagree
 - Score 4 = strongly disagree
6. The volume of your hair after treatment is fine.
 - Score 1 = strongly agree
 - Score 2 = agree
 - Score 3 = disagree
 - Score 4 = strongly disagree

9.4.8. Assessment of the hair and scalp (diagnostic combing)

An assessment of the hair and scalp will be performed to determine the number of live lice in the hair with a special lice comb (dry combing). The lice comb will be provided by Oystershell (OYS internal code: 07080019).

For this assessment, the hair will be divided into 3 sections: left, middle, and right side of the head. Each section will be combed 6x with a lice comb and the number of live lice encountered per section is recorded. The hair will be assessed for lice on day 0 to determine if the subject complies with the inclusion criterion: ≥ 5 live lice. This procedure will be repeated for all visits before and after treatment.

The life stage of lice found during assessments on all visits must be recorded as this is necessary for determination of re-infestation (see chapter 9.5). In case that the examination on day 1, 2, 7 or day 10 will show active head lice infestation, the lice caught by the comb will be discarded. The subjects with active head lice infestation on day 10 will be considered a treatment failure and will receive an appropriate treatment.

9.5. Efficacy measurements

The endpoints for efficacy assessment will be based on the cure rate on day 10 p.a. The cure rate is defined as proportion of subjects without any live lice, corrected for the rate of reinfestation. A re-infestation [16] is defined as:

- a) no adult lice or third stage nymphs present following the first treatment AND
- b) no more than two adult lice or third stage nymphs found by combing on day 10.
- c) Safety measurements

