5. OBJECTIVES & ENDPOINTS

5.1. Primary objective

The primary objective of this study is to demonstrate that the cure rate after local application of test product is better than a predefined limit. The test product must achieve a cure rate superior to 70% (at the end of day 10, corrected for re-infestation).

To compare efficacy and safety of test product against reference product in subjects, infested with head lice (*Pediculus humanus capitis*).

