6.5. Final evaluation visit (Day 10 + 2 days)

The final visit will be performed on study day 10 (+2 days). The final visit examination is performed to verify if the subject is cured. A subject will be considered cured, if no living head lice could be detected. If living lice present on day 10, the life stages of the lice will be documented. If any other pediculicidal agents was employed during the observation period, the subject will be considered a treatment failure (no efficacy analysis will be performed).

The following examinations will be performed within the final visit:

- Hair scalp assessment for living lice (all stages) by study staff (see chapter 9.4.8)
- Assessments of skin and eyes irritation, global tolerability, local tolerability
- Questioning on well-being
- Registration and documentation of any adverse events and/or changes regarding concomitant diseases, concomitant medication, withdrawal criteria
- Questionnaire on the satisfaction with the esthetical effect of the products
- Vital signs

In case that the examination (diagnostic combing) will show active head lice infestation (living nymph or imago), the subject will be considered treatment failure or re-infestation and will receive the standard of care at the site.

Subjects exhibiting either subjective or objective abnormalities when the trial has been completed will be followed up. Any AE which remains unresolved after completion of the trial requires detailed evaluation and follow-up until the AE has been resolved or a reasonable explanation for its persistence is found. If the subject refuses to follow the instructions of the study staff, the latter is released from responsibility.

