10.4.1. Analysis of primary objective

The cure rate (p) corresponds to the proportion of subjects who are cured at day 10 among all subjects that received any treatment at day 0. The aim of the study is to show superiority for the cure rate of the test product versus a predefined limit of 70%.

The following null hypothesis will be tested:

$$H_{0, \text{prim}}: p_T - p_R = 0 \text{ and } H_a: p_T - p_R > 15\%$$

A χ^2 -test of independence will be used to test the null hypothesis.

In case superiority could not be proven, non-inferiority will be tested. According to ICH guideline “Points to consider on switching between superiority and non-inferiority” [17], it is allowed to assess non-inferiority in to the absence of superiority. Prerequisites include:

- predefinition of a non-inferiority margin
- no correction in terms of multiplicity

As non-inferiority margin (δ), a 7.5% worse cure rate is regarded as clinically not relevant. The following null hypothesis will be used: $H_{0, \text{NI}}: p_T - p_R < \delta$, whereby $\delta = -7.5\%$. The lower, 95% confidence interval (CI) of the difference $p_T - p_R$ will be used for the test. If $H_{0, \text{NI}}$ will be rejected, non-inferiority cannot be shown.

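### The primary Day 10 cure rate is corrected for re-infestation, but the plan never says how a re-infested subject counts, section 9.4.8 cancels the correction, and the 9.5 rule leaves young live nymphs unlimited

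*Combined protocol and SAP*

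**What the plan says.** The correction belongs to the primary objective in section 5.1: "The test product must achieve a cure rate superior to 70% (at the end of day 10, corrected for re-infestation"). Section 5.3 repeats it in the primary endpoint: "cure rate at the end of day 10 (corrected for re-infestation) for the test product". Section 9.5 defines the cure rate as the "proportion of subjects without any live lice, corrected for the rate of reinfestation". It then defines a re-infestation by two conditions that must both hold. Condition (a) reads "no adult lice or third stage nymphs present following the first treatment AND". Condition (b), which concerns the final visit, reads "no more than two adult lice or third stage nymphs found by combing on day 10".

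Four other places bear on how the outcome is scored:

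- Section 6.5 first says "A subject will be considered cured, if no living head lice could be detected". It then says that, if the combing "will show active head lice infestation (living nymph or imago), the subject will be considered treatment failure or re-infestation".
- Section 9.4.8 requires life stage to be recorded at all visits so that re-infestation can be determined, and refers to 9.5. Its closing sentence nevertheless classes subjects with active infestation on Day 10 as treatment failures, with no exception.
- Section 10.4.1 defines the cure rate as the "proportion of subjects who are cured at day 10 among all subjects that received any treatment at day 0" and does not mention the correction.
- Section 8.6.1 requires at least 5 live lice and 5 apparently live nits at entry. Section 2 gives 1-2 weeks for eggs to hatch and 7-10 days for a nymph to become adult.

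**The concern.** Section 9.5 says which subjects are re-infested but not what the correction does with them. Three treatments are open: count them as cured, count them as failed, or remove them from the denominator. If 9.4.8 is followed, they are all failures and the correction required by 5.1, 5.3 and 9.5 has no effect. The primary cure rate therefore cannot be computed in one way from the text.

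The classification is also loose. Condition (b) caps adults and third-stage nymphs at two but says nothing about younger stages. A subject who meets (a) and carries only first- or second-stage live nymphs on Day 10 satisfies the rule literally. Such nymphs are what eggs surviving the treatment would produce, so an ovicidal failure can be labelled re-infestation. Condition (a) also names no visit: the post-treatment check on Day 0, Day 1, Day 7 before the second application, or all of these would fit.

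At stake are the comparison with the fixed 70% limit and the between-arm comparison. Both would depend on a choice that could be made after the results are known.

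**Working it through.** **1. The passages side by side, for a subject who meets condition (a)**

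| Live lice on Day 10 | Section 9.5 | Section 6.5 | Section 9.4.8 |
|---|---|---|---|
| First- or second-stage nymphs only | re-infested (literal reading) | failure or re-infestation | failure |
| 1-2 adults or third-stage nymphs | re-infested | failure or re-infestation | failure |
| 3 or more adults or third-stage nymphs | not re-infested | failure or re-infestation | failure |

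In the first two rows, 9.5 and 9.4.8 give different answers. If (a) is not met, nobody is re-infested.

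**2. Why young nymphs matter.** An egg that survives the Day 7 application and hatches afterwards gives a nymph aged at most 10 − 7 = 3 days on Day 10, or 12 − 7 = 5 days at the end of the visit window. Section 2 gives 7-10 days to adulthood. Such a failure therefore tends to appear in the early stages that (b) does not mention. Surviving eggs do not breach (a), which concerns only adults and third-stage nymphs.

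**3. Effect on the 70% criterion.** The documents give no re-infestation rate and name no test against 70%. Assumptions: n = 35 in the test arm (section 8.1), exact one-sided binomial test, p = P(X ≥ x | n, 0.70). Counts are illustrative.

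| Louse-free + re-infested | Counted as failed | Excluded | Counted as cured |
|---|---|---|---|
| 28 + 2 | 28/35 = 80.0%, p = 0.133 | 28/33 = 84.8%, p = 0.041 | 30/35 = 85.7%, p = 0.027 |
| 28 + 3 | 28/35 = 80.0%, p = 0.133 | 28/32 = 87.5%, p = 0.019 | 31/35 = 88.6%, p = 0.009 |

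At one-sided 5%, two subjects decide the result in the first row. At one-sided 2.5% none of the three readings succeeds there, but three subjects decide it in the second row.

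At the planned 95%, expected failures are 35 × 0.05 = 1.75. If an assumed 20% of failures were credited as cured, the rate becomes 0.95 + 0.05 × 0.20 = 0.96. The chance of success rises from 99.3% to 99.8% (cut-off 30/35, one-sided 5%) or from 97.1% to 98.8% (cut-off 31/35, one-sided 2.5%). At an assumed true rate of 85%, the same 20% gives 0.88, and success rises from 56.9% to 76.2% or from 38.1% to 58.8%.

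**4. Effect on the between-arm comparison.** First, the plan's own figure (section 10.2: 95% v 55%, margin 15%, 80% power, 5% level, 30 per group). With unpooled variance:

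n = (1.645 + 0.842)² × (0.95 × 0.05 + 0.55 × 0.45) / (0.40 − 0.15)² = 6.18 × 0.295 / 0.0625 = 29.2, so 30.

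This reproduces the plan at one-sided 5%; one-sided 2.5% would need 38. The same method at n = 35, one-sided 5%, uses power = Φ[(pT − pR − 0.15)/SE − 1.645]:

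- No failures credited, 95% v 55%: SE = √(0.295/35) = 0.0918; 0.25/0.0918 = 2.723; power 86%.
- 10% credited in both arms, 95.5% v 59.5%: SE = 0.0901; 0.21/0.0901 = 2.331; power 75%.
- 20% credited in both arms, 96% v 64%: SE = √(0.2688/35) = 0.0876; 0.17/0.0876 = 1.940; power 62%.

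The loss arises because the reference arm has more failures to credit: 35 × 0.45 = 15.75 against 1.75.

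**The case against.** Several arguments on the other side have weight.

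- A reader might infer from (b), which has no lower bound, that even a louse-free head would be called re-infested. The documents do not support this. Section 6.5 calls such a subject cured, and only heads with live lice reach the split between failure and re-infestation.
- A reader might also say that 10.4.1 contradicts the correction. It does not; it is silent. It uses the word cured without redefining it, so 9.5 could supply the meaning. The direct contradiction is 9.4.8 against 6.5 and 9.5.
- Condition (b) has a natural reading: the only lice found are one or two late-stage ones. Recording life stage fits that intent, and the definition is taken from a cited publication that was not available for this review. This stands as a likely intent, but the sentence does not say it. Even on that reading, how such a subject counts stays open.
- The biology is only suggestive. The documents give no duration for each nymph stage. If, as an assumption, three equal stages filled 7 days, the third would begin at about 4.7 days (7 × 2/3), so a nymph 5 days old at a Day 12 visit could already be third stage. This limits what a stage rule can achieve; it does not remove the gap in (b).

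**Conclusion.** The point holds. The correction in the primary endpoint has no stated effect on a subject's outcome, 9.4.8 nullifies it, and 9.5(b) read literally admits young live nymphs when (a) is met. This should be fixed before analysis, but it is not evidence that the trial would reach a wrong conclusion.

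A reader might infer that the gap simply favours the test product, or that it matters only if the cure rate falls well below plan. Neither follows. Crediting re-infested subjects as cured can only raise the rate compared with 70%, and at a true 95% that gain is negligible. In the between-arm test the same credit works against the test product even at the planned rates: about 86% power falls to 75% or 62% if 10% or 20% of failures are credited in both arms.

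These figures rest on assumed re-infestation counts and shares, equal shares in both arms, 35 subjects per arm, an exact binomial test for the 70% limit, and a normal approximation with the 15% margin at one-sided 5% for the comparison. The textual contradiction does not depend on any of them.

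**What to change.** Before database lock:

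1. State in 9.5 and 10.4.1 one rule for how a re-infested subject counts, in both numerator and denominator.
2. Reconcile 6.5 and 9.4.8 with that rule.
3. In 9.5, name the visits that condition (a) covers. Require that the only live lice on Day 10 are one or two adults or third-stage nymphs. Count every other subject with a live louse on Day 10 as a failure.
4. Report the uncorrected cure rate, with every Day 10 infestation a failure, beside the corrected one for both arms.

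Database lock is a better deadline than unblinding, because subjects and the staff who apply the products know the treatment (section 8.3).

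The cost is wording in four sections and one extra table row per arm; life stage is already recorded at every visit. The corrected rate may be slightly less favourable, and a few true re-infestations may be scored as failures. Without a duration for each nymph stage, the stage rule reduces misclassification but may not remove it at a Day 12 visit.
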